Appendix A

List of Abbreviations

ACOG American Congress of Obstetrics and Gynecology

CRF Case Report Form

DSMB Data Safety Monitoring Board

FDA U. S. Food and Drug Administration

GCP Good Clinical Practice

ICH International Conference on Harmonisation

IOL Induction of Labor

IRB Institutional Review Board

PK Pharmacokinetic

PD Pharmacodynamic

Background

[REDACTED]

[REDACTED]

[REDACTED]

|||||

Rationale and Specific Aims

The primary objective of this proposal is to compare the efficacy and safety of vaginal and buccal misoprostol for women undergoing labor induction at greater than or equal to 37 +0 completed weeks gestation. The secondary objective of this proposal is to assess the PK parameters with these two routes of administration in a subcohort of this trial. The long-term objective of this line of research is to inform providers' clinical decision making for the large number of women having labor induction. By providing robust PK and PD clinical outcomes data for these two routes of administration, clinicians will be informed for evidence-based decisions.

The 3 Specific Aims of this trial are:

1. To compare the efficacy and safety of 25 mcg of misoprostol initially followed by 50mcg thereafter administered by either buccal or vaginal route in a placebo-controlled, double blind RCT. We will recruit women at term undergoing labor induction to accomplish this trial.
2. To compare the PK parameters of 25 mcg and 50 mcg of misoprostol administered by either buccal or vaginal routes. Further, we will analyze the clinical outcomes in Aim 1 based on the PK parameters, controlling for patient characteristics, to assess the impact of PK parameters on clinical success of this drug. In this way, we hope to comment on the strategic dose and individualized dosing model potential for labor induction with misoprostol.

3. To compare the trial participant satisfaction with each route of administration to improve patient-based outcomes. This will be done by administering a satisfaction survey at the end of the trial. As participants will have study drug placed both buccally and vaginally, they will be uniquely able to comment on comfort and preference for route of delivery.

Population and Study procedure

[REDACTED]

Inclusion/Exclusion Criteria

The following are inclusion criteria for the IMPROVE study.

Inclusion Criteria:

Statistical Considerations

In our preliminary retrospective analysis of our institutional data over the last 1-2 years, there was just over a 4 hour difference in the time to delivery between the routes of administration. This was confirmed using a survival estimate for the two groups, with buccal misoprostol having a median time to delivery of 16.95 hours and vaginal 12.78 hours. In order to demonstrate a significant difference in a non-inferiority test of two survival curves with a limit of 4.5 hours, we will need 143 women in each group (see table below). We will recruit 300 women total to accommodate up to 5% withdrawals. We do not anticipate loss to follow-up as once women begin an induction, it is extremely rare that induction is terminated. Women remain admitted to labor and delivery until they are discharged after delivery.

Non-inferiority test for two exponential survival curves (Nquery), 80% power at a .05 significance level:

Limit	4 hours	4.25 hours	4.5 hours	5 hours
Maximum follow-up	60 hours	60 hours	60 hours	60 hours
Denominator lambda	.0409	.0409	.0409	.0409
Median survival (buccal)	16.95	16.95	16.95	16.95
Median survival (vaginal)	12.95	12.7	12.45	11.95
Non-inferiority limit on hazard ratio	1.309	1.335	1.361	1.418
N per group	187	163	143	111
Total number of events (vaginal births required)	341	296	260	203
N per group if Null hypothesis is true	183	158	139	108

We plan to analyze the primary outcome using survival curve analysis due to the possibility of cesarean delivery truncating the time to delivery. All outcomes will be compared using an intent-to-treat methodology. Discrete outcomes will be compared using chi-square testing and continuous variables will use appropriate parametric and nonparametric tests.

PK analysis will follow standard techniques for comparison of standard parameters and will be fitted to the most appropriate compartmental model. Our investigator team has the expertise to perform these analyses and has a large body of experience with pregnancy pharmacology studies.

Privacy/Confidentiality Issues

[REDACTED]

Follow-up and Record Retention

[REDACTED]

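### The trial is sized as a non-inferiority test against a hazard ratio of 1.361, but the sizing sentence speaks of a significant difference, the analysis paragraph drops the limit, and the 80% power makes no allowance for cesareans

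*Combined protocol and SAP*

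**What the plan says.** All of this is in Statistical Considerations.

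- **Sizing sentence:** "In order to demonstrate a significant difference in a non-inferiority test of two survival curves with a limit of 4.5 hours", followed by 143 women per group. Recruitment is 300 in total, to cover up to 5% withdrawals.
- **Table title:** "Non-inferiority test for two exponential survival curves (Nquery), 80% power at a .05 significance level". The 4.5-hour column has 1.361 in the row "Non-inferiority limit on hazard ratio", 260 in the row for events, which are counted as vaginal births, and 139 in the row "N per group if Null hypothesis is true". Follow-up is capped at 60 hours.
- **Analysis paragraph:** "We plan to analyze the primary outcome using survival curve analysis due to the possibility of cesarean delivery truncating the time to delivery". It gives no limit, confidence level, direction or success rule. The sentence after it says that all outcomes are compared by intention to treat.

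The visible text does not say whether the .05 is one- or two-sided, or at which true HR the 80% applies. Under Rationale and Specific Aims, the primary objective and the numbered aims speak only of comparing the routes.

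**The concern.** A significant difference and non-inferiority are separate conclusions with separate cut-offs. The first asks whether an HR of 1 can be excluded; the second asks whether an HR of 1.361 or worse can be excluded. The trial is sized for the second, but the words used for its purpose belong to the first, and the analysis paragraph does not say which will be tested. An analyst following that paragraph could run an ordinary comparison of the curves and report a significant or non-significant difference, leaving the question that fixed the sample size unanswered.

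The stated power raises a related problem. The 80% depends on 260 vaginal births. The same section expects cesareans to cut some times short, but the step from events to women leaves no room for them.

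**Working it through.** **Inputs (all from the sample-size table).** Buccal hazard 0.0409 per hour, which is ln 2/16.95 and is the denominator of the ratio, so the HR is vaginal:buccal. In the 4.5-hour column the vaginal median is 12.45, and 16.95/12.45 = 1.361. Follow-up 60 h, alpha .05, power 80%.

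**1. Reproducing the plan's figures.** Try a true HR of 1 and one-sided .05.

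- Events = 4(1.645 + 0.842)² / (ln 1.361)² = 260.3 (table 260).
- Probability of an event by 60 h at the buccal hazard = 1 − exp(−0.0409 × 60) = 0.914.
- N per group = 260.3 / (2 × 0.914), rounded up = 143 (table 143).
- N with the vaginal hazard 1.361 times as high: 260.3 / (0.914 + 0.965), rounded up = 139 (table 139). With vaginal slower instead, the result is 149, which does not match. The limit therefore concerns buccal being the slower route.

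| Limit | Events, computed (table) | N per group, computed (table) | N under null, computed (table) |
|---|---|---|---|
| 4 h | 341.1 (341) | 187 (187) | 183 (183) |
| 4.25 h | 296.2 (296) | 163 (163) | 158 (158) |
| 4.5 h | 260.3 (260) | 143 (143) | 139 (139) |
| 5 h | 202.8 (203) | 111 (111) | 108 (108) |

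Two-sided .05 at a true HR of 1 would need 331 events and 181 per group in the 4.5-hour column, which does not match. The sizing arithmetic is right.

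**2. Two tests, two cut-offs, with 260 events.** SE of ln HR = 2/√260 = 0.124.

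- Non-inferior (upper bound of the 90% CI below 1.361): observed HR at most exp(ln 1.361 − 1.645 × 0.124) = 1.110.
- Significantly different with vaginal faster (two-sided .05): observed HR at least exp(1.96 × 0.124) = 1.275.

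Between 1.110 and 1.275 the result is non-significant but fails non-inferiority. The probability of landing there is 17.5% at a true HR of 1 and 40% at a true gap of 2 h (exponential curves, buccal median 16.95 h).

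If a non-significant result were taken as non-inferiority, the error at the limit would be Φ(1.96 − ln 1.361/0.124) ≈ 0.30, against the designed 0.05.

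**3. Cesareans and the 80%.** 286 × 0.914 ≈ 261 vaginal births. That uses up the whole 286 with 60-hour administrative censoring as the only loss. The documents give no cesarean rate, so a range is assumed. Let a share p of all exits be cesareans, occurring independently and censoring the time to vaginal birth. Then

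vaginal births = 286 × (1 − p) × [1 − exp(−0.0409 × 60/(1 − p))]

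power at HR 1 = Φ(√E/2 × ln 1.361 − 1.645)

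| p (assumed) | Vaginal births, E | Power at HR 1 |
|---|---|---|
| 10% | 241 | 77% |
| 20% | 218 | 74% |
| 30% | 194 | 69% |

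The cesarean share is not the share of events lost. At p = 20%, 218 instead of 260 is 16% fewer (42/260), because some of the women delivered by cesarean would have been censored at 60 h anyway.

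**The case against.** **The wording is loose, not contradictory.** The sizing sentence names the non-inferiority test and its limit in the same clause as the significant difference, and the table title repeats the test. This stands as far as intent goes. A reader might infer that the trial aims at superiority; the documents do not support that, since the phrase is in the sizing sentence and the objective and aims say only that the routes are compared. But intent is not a decision rule, and no visible sentence carries the limit into the analysis.

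**A survival analysis can include a confidence interval set against 1.361.** True. The plan does not exclude the right test; it fails to specify it.

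**The direction is already visible.** Also true: the table sets buccal at 16.95 against vaginal at 12.45. Only an explicit sentence is missing.

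**The 30% error is hypothetical.** It requires a misreading that the plan never proposes. It also holds events at 260; at the limit, 143 per group would give about 269 events and 28.5%. The figure shows what a written rule would prevent, not what the plan would do.

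**The retrospective gap.** The paragraph opens with "buccal misoprostol having a median time to delivery of 16.95 hours and vaginal 12.78 hours", an HR of 16.95/12.78 = 1.326, where non-inferiority power is only about 8%. A reader might call the trial underpowered for that reason. That does not follow: sizing at a true HR of 1 is conventional, and low power so close to the limit is expected. Whether to print power at that gap is a matter of preference.

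**Redaction.** Background and the study procedures are blacked out, so a hypothesis statement could be there. This limits what can be said about unstated sidedness and true HR. It does not rescue the analysis paragraph, which is not visibly redacted at these sentences.

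**The 300 recruited give a margin.** Only if few withdraw. With no withdrawals at all, cesarean shares of 10%, 20% and 30% give power of 79%, 75% and 71%.

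**Conclusion.** The point holds and should be fixed. The sample size is arithmetically correct for a one-sided .05 non-inferiority test at a true HR of 1; those two settings are inferred from the match across all four columns, not quoted. The sizing sentence misnames that test, and the analysis paragraph does not carry its limit forward. The practical consequence is the band of observed HRs from 1.110 to 1.275, in which the text as written would report no significant difference while the sized test fails.

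The 80% is conditional on 260 vaginal births and is not delivered by 286 women once cesareans occur: about 77%, 74% or 69% at assumed cesarean shares of 10%, 20% or 30%. This rests on cesareans being treated as censored, as the table's event count and the analysis sentence imply, on exponential curves, and on cesarean timing being independent of time to vaginal birth. The documents do not support a claim that the N is miscalculated or that the design is a superiority trial.

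**What to change.** 1. In the sizing sentence, replace the wording about a significant difference with: *to test whether buccal is non-inferior to vaginal*. The sponsor should confirm that this is the tested route, as the table implies.
2. Add to the analysis paragraph: *The HR is vaginal:buccal. Buccal is non-inferior if the upper bound of the two-sided 90% CI is below 1.361. A non-significant difference is not evidence of non-inferiority.*
3. Restate the power: *80% at a true HR of 1, one-sided .05, if 260 vaginal births are observed*. Add the lower figure at the site's expected cesarean rate, computed with the formula above and not by treating that rate as the percentage of events lost.

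Whether the 4.5 hours or the HR of 1.361 governs if the two diverge is for the sponsor to decide; the rule in item 2 assumes the HR.

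The cost is a few sentences. N does not change. The downside is a less favourable stated power, and the plan would acknowledge that a trial can end with neither a difference nor non-inferiority shown.
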